15.4.2 Serious Adverse Event (SAE)

A serious adverse event is an undesirable sign, symptom or medical condition which:

- is fatal or life-threatening;
- requires or prolongs inpatient hospitalization;
- results in persistent or significant disability/incapacity;
- constitutes a congenital anomaly or birth defect; or
- jeopardizes the participant and requires medical or surgical intervention to prevent one of the outcomes listed above.

Events **not** considered to be serious adverse events are hospitalizations for:

- routine treatment or monitoring of the studied indication, not associated with any deterioration in condition, or for elective procedures
- elective or pre-planned treatment for a pre-existing condition that did not worsen
- emergency outpatient treatment for an event not fulfilling the serious criteria outlined above and not resulting in inpatient admission respite care

15.4.3 Expectedness

- **Expected:** Expected adverse events are those that have been previously identified as resulting from administration of the agent. For the purposes of this study, an adverse event is considered expected when it appears in the current adverse event list, the Investigator's Brochure, the package insert or is included in the informed consent document as a potential risk.
- **Unexpected:** An adverse event is considered unexpected when it varies in nature, intensity or frequency from information provided in the current adverse event list, the Investigator's Brochure, the package insert or when it is not included in the informed consent document as a potential risk

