3.1 Eflornithine (NSC-337250) (103678.)

a. DESCRIPTION

This trial will use low dose oral eflornithine hydrochloride. Eflornithine is a member of the following drug classes: 1) inhibitor of ornithine decarboxylase (ODC), 2) hair growth retardant. Eflornithine is FDA approved as a cream for female hirsutism, and in intravenous form for trypanosomiasis. The oral tablet form is not available outside of the clinical trial setting in the U.S. The formulation used in this trial is similar to that reported previously in a Phase III colon adenoma clinical trial in combination with sulindac.[28] This formulation of eflornithine is under study in U.S. and international trials both for chemoprevention (low dose) and cancer therapy (high dose). (See Appendix).

b. TOXICOLOGY

Contraindications: Prior hypersensitivity to eflornithine. Precaution in patients with bone marrow suppression or hematologic disorders.

Side effects: The side effects reported herein are those observed in all studies to date, and for both high and low dosing. This study will utilize the low dose of eflornithine (500mg per day).

Common Side Effects (most frequently reported AEs in NCI, DCP-sponsored chemoprevention studies): diarrhea (9.0%), headache (7.5%), nausea (6.5%), hearing loss (5.6%), tinnitus (4.3%) and asthenia (4.7%).

Less Common Side Effects (2 – 3%): epigastric pain, flatulence, dyspepsia, anemia, dizziness and skin rash.
Rare Side Effects (1 - 2%): stomatitis, rhinitis, insomnia, infections, vomiting, vasodilation, dry mouth, constipation, dry skin, menstrual disorders, pharyngitis, emotional lability, pruritis, myalgia, and pain (miscellaneous).

There have been rare but serious reports of seizures in some subjects receiving high doses of eflornithine (15 g/day, ~215 mg/kg-bw/day). These instances occurred in subjects who were trypanosomiasis, glioma, or AIDS patients, and were suspected of having an impaired blood-brain barrier due to their disease or prior drug treatments.

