15.5.2 Serious Adverse Event Reporting

All serious adverse events, regardless of causality to study drug, will be reported to the Principal Investigator and/or the Study Coordinator at each institution, and also to the Coordinating Center.

All serious adverse events must be reported to the Coordinating Center within 24 hours of the site becoming aware of the event. Events should be reported using the Vanderbilt Coordinating Center SAE form, located in the packet of supplemental forms. This form must be fully completed and emailed (preferred), faxed, or scanned to:

If SAE documents are faxed, the Coordinating Center must be notified via email as well. Follow-up information must also be reported within 24 hours of receipt of the information by the investigator.

The Coordinating Center will disseminate information regarding serious adverse events to the participating sites as described in FDA guidance only in the case that the event(s) is/are unexpected, and is/are believed to be related (i.e., possibly, probably or definitely) to the study device/medication. The Coordinating Center will be responsible for reporting of events to the FDA and supporters, as appropriate (outlined below).

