15.5.4 Food and Drug Administration (FDA)

In this trial, unexpected serious adverse events believed to be definitely, probably, or possibly related to study treatment (as determined by the sponsor-investigator) will be reported to the FDA via MedWatch 3500A (available at <https://www.fda.gov/downloads/AboutFDA/ReportsManualsForms/Forms/UCM048334.pdf>).

Submissions by the Sponsor can be submitted via fax or email and must be addressed to Regulatory Project Manager in the FDA review division that has responsibility for review of the IND. The Sponsor, Cancer Prevention Pharmaceuticals, will be responsible for reporting to the FDA as appropriate.

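### Section 15.4.3 lets the same serious adverse event be both expected and unexpected, with no rule for which prevails, and that label decides the FDA report and the notice to other sites

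*Combined protocol and SAP*

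**What the plan says.** Section 15.4.3 has two bullets. The first states that "an adverse event is considered expected when it appears in the current adverse event list". It gives three alternatives to that list: the Brochure, the package insert and the consent form. Appearing in any one of the four sources is enough. The second begins "An adverse event is considered unexpected when it varies in nature, intensity or frequency from information provided in the current adverse event list". It then names the Brochure and the package insert as well, and adds absence from the consent form as a separate ground for calling an event unexpected. No sentence ranks the bullets.

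The *current adverse event list* is not defined. The only side-effect list in the protocol is in section 3.1, which says of itself: "The side effects reported herein are those observed in all studies to date, and for both high and low dosing". On the package insert, section 3.1 also says: "The oral tablet form is not available outside of the clinical trial setting in the U.S". Appendix 17.1 shows an approved injectable and an approved cream, plus an oral form whose EU orphan listing was withdrawn in 2003.

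Two reporting routes use the label. Section 15.5.4 sends to the FDA those serious events that are unexpected and at least possibly related. Section 15.5.2 passes information to participating sites only under the same two conditions. On who files, 15.5.2 says "The Coordinating Center will be responsible for reporting of events to the FDA and supporters, as appropriate", while 15.5.4 says "The Sponsor, Cancer Prevention Pharmaceuticals, will be responsible for reporting to the FDA as appropriate".

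**The concern.** A definition of expectedness has to place each event in one class. Here the *expected* bullet asks only whether the event appears somewhere, while the *unexpected* bullet asks whether it matches what was described and whether participants were told of it. These are different questions, so one event can pass both. Two people classifying the same event could reach opposite answers, and each would be following the protocol.

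At stake is whether a related serious event reaches the FDA as an unexpected event and whether the other sites hear of it. This is a double-blind prevention trial with up to three sites. No other section provides for telling one site about an event at another.

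**Working it through.** There is no stated figure to reproduce. The check is on the logic of the two bullets.

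**Notation.** L: the event appears in the adverse event list, the Brochure or the package insert. C: it appears in the consent form. V: it differs in nature, intensity or frequency from the listed information.

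- Bullet 1: expected if L or C.
- Bullet 2: unexpected if V or not C.

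**Assumption.** An event in none of the L sources counts as differing in nature. That leaves four combinations with L and two without, six in all.

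| Event | Bullet 1: expected? | Bullet 2: unexpected? | Result |
|---|---|---|---|
| L, C, not V | yes | no | expected only |
| L, C, V (for example, more severe than described) | yes | yes | both |
| L, not C, not V | yes | yes | both |
| L, not C, V | yes | yes | both |
| not L, C | yes | yes (by the assumption) | both |
| not L, not C | no | yes | unexpected only |

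Four of six case types meet both definitions. If the assumption is rejected and a consent-only event is treated as not differing, that row becomes expected only and the count is three of six. These are counts of case types and say nothing about how many events would fall in each.

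**Can the second bullet be applied to the material in the protocol?** Suppose, for illustration, that the section 3.1 text is the intended list. It has 6 common, 6 less common and 15 rare terms: 6 + 6 + 15 = 27. Each has a percentage or a frequency band, and none has a grade. A comparison of intensity therefore has no stated reference level there. A comparison of frequency is possible in aggregate, but a single case rarely shows a changed frequency.

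Section 3.1 separately describes seizures at 15 g/day. The trial dose is 500 mg/day, and 15,000 / 500 = 30. Neither bullet mentions dose, so a seizure in this trial would be expected under bullet 1 on this reading, and unexpected only if someone judged it to differ from that description.

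**Which routes depend on the label?**

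| Route | Section | Depends on expectedness? |
|---|---|---|
| Site to Coordinating Center, 24 hours | 15.5.2 | no |
| Coordinating Center to sponsor, 24 hours | 15.5.5 | no |
| IRB/EC, under institutional standards | 15.5.3 | no |
| FDA | 15.5.4 | yes |
| Notice to participating sites | 15.5.2 | yes |

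The exposure is confined to the last two rows.

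**Who decides and who files?** Section 15.5.2 gives FDA reporting to the Coordinating Center, and 15.5.4 gives it to the sponsor. Section 15.5.4 also leaves the decision on relatedness to a sponsor-investigator, although section 3.0 says that the company holds the IND. No section clearly says who decides expectedness.

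**The case against.** The best defence is that 15.4.3 should be read as a whole. On that reading the second bullet qualifies the first: a listed event that is more severe than described is unexpected, and the intent is clear. This has force. A reader might infer from the first bullet alone that any serious event becomes expected at any grade once its term is listed, so that every term in section 3.1 escapes expedited reporting. The documents do not support that, because the second bullet covers deviation in intensity. Nor are the bullets simple opposites. They agree on an event that is listed, in the consent form and unchanged, and on an event found in no source.

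The seizure example is also weaker than it looks. Section 3.1 ties those reports to trypanosomiasis, glioma or AIDS patients suspected of an impaired blood-brain barrier, so a seizure in a participant without those conditions could readily be judged different in nature. Nor does the protocol say that section 3.1 is the list meant in 15.4.3, and its common percentages come from chemoprevention studies. The contents of the Brochure and consent form cannot be judged here.

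A reader might further infer that serious events could go unreported altogether. They would not: all of them reach the Coordinating Center and the IND-holding sponsor whatever the label. Under 15.1 a DSMB receives reports every six months and may see any data it needs, and the DSMC also oversees safety.

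Finally, the sentence in 15.5.2 about FDA reporting points onward to later text, where the sponsor is named. This softens the conflict over the filing party but does not remove it.

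What remains is the missing precedence rule. Reading the second bullet as controlling is sensible, but the text does not say so. The sponsor's receipt of every event does not cure this, because the label still decides whether the FDA report is made.

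**Conclusion.** The point holds as an internal inconsistency in a safety-reporting rule. Four of six case types (three on the narrower assumption) meet both definitions. The clearest are a related serious event that is listed but more severe than described, and one that is in the Brochure but absent from the consent form. Either could be labelled expected, consistently with the text, and so miss the FDA report and the notice to other sites.

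The conclusion rests on the wording of 15.4.3, 15.5.2 and 15.5.4 alone. It does not depend on section 3.1 being the intended list, nor on what the Brochure or consent form contains. The undefined list and the unclear package insert make the rule harder to apply. The number of events affected cannot be estimated from the documents. The point warrants correction; the reports that do not depend on the label limit its seriousness.

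**What to change.** Amend 15.4.3 so that the two definitions exclude each other:

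- An event is expected only if it is listed in one named, current reference safety document and is consistent with it in nature and intensity. Otherwise it is unexpected.
- Where the bullets or sources disagree, *unexpected* prevails.
- Define *current adverse event list* and *package insert* for this oral tablet, or drop them.
- Say whether the consent form still counts. If it is simply removed, an event that is in the reference document but not in the consent form, now unexpected under the second bullet, would become expected.
- Say whether frequency remains a criterion, and who assesses it across cases.

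Reconcile 15.5.2 with 15.5.4 so that one named party is responsible for the determination and for the FDA report.

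The choice of reference document belongs to the sponsor. The documents do not show whether the Brochure is organised by dose, so the rule should not presume it.

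The cost is an amendment and possibly a few more expedited reports. No new data, visits or analyses are needed.

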15.4.4 Attribution

Attribution is the relationship between an adverse event or serious adverse event and the study treatment. Attribution will be assigned as follows:

- **Definite** – The AE is clearly related to the study treatment
- **Probable** – The AE is likely related to the study treatment
- **Possible** – The AE may be related to the study treatment
- **Unlikely** - The AE is doubtfully related to the study treatment
- **Unrelated** - The AE is clearly NOT related to the study treatment

15.5 Adverse Event Reporting methods.

15.5.1 General Considerations

Investigators should use correct medical terminology/concepts when reporting AEs or SAEs, and avoid colloquialisms and abbreviations. If known at the time of reporting, a diagnosis should be reported rather than individual signs and symptoms (e.g. record only liver failure or hepatitis rather than jaundice, asterixis, and elevated transaminases). However, if a constellation of signs and/or symptoms cannot be medically characterized as a single diagnosis or syndrome at the time of reporting, it is acceptable to report the information that is currently available. If a diagnosis is subsequently established, it should be reported as follow-up information.

All deaths that occur during the protocol-specified AE reporting period, regardless of attribution, will be reported to the appropriate parties. When recording a death, the event or condition that caused or contributed to the fatal outcome should be reported as the single medical concept. If the cause of death is unknown and cannot be ascertained at the time of reporting, report "Unexplained Death." Deaths that occur during the protocol specified adverse event reporting period that are attributed by the investigator solely to progression of disease should be recorded only in the study eCRF and not reported as an SAE.

A pre-existing medical condition is one that is present prior to initiation of protocol specified treatment. Such conditions should be reported as medical and surgical history. A pre-existing medical condition should be re-assessed throughout the trial and reported as an AE or SAE only if the frequency, severity, or character of the condition worsens during the study. When reporting such events, it is important to convey the concept that the pre-existing condition has changed by including applicable descriptors (e.g., "more frequent headaches").

Any AE that results in hospitalization or prolonged hospitalization should be documented and reported as an SAE. If a patient is hospitalized to undergo a medical or surgical procedure as a result of an AE, the event responsible for the procedure, not the procedure itself, should be reported as the SAE. For example, if a patient is hospitalized to undergo coronary bypass surgery, record the heart condition that necessitated the bypass as the SAE.

Hospitalizations for the following reasons do not require reporting:

- Hospitalization or prolonged hospitalization for diagnostic or elective surgical procedures for pre-existing conditions; or
- Hospitalization or prolonged hospitalization required to allow efficacy measurement for the study; or
- Hospitalization or prolonged hospitalization for scheduled therapy of the target disease of the study.

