15.5.5 Reporting to the Sponsor

The Coordinating Center will submit all SAEs, regardless of causality, to Cancer Prevention Pharmaceuticals (CPP) within 24 hours of the Coordinating Center becoming aware of the event.

15.6 Reporting Pregnancy, Fetal Death, and Death Neonatal Pregnancy.

Study participants who become pregnant while on study; that pregnancy should be reported to the Coordinating Center using the Vanderbilt Coordinating Center SAE form within 24 hours of the site becoming aware.

Fetal Death. Fetal Death defined in CTCAE as “A disorder characterized by death in utero; failure of the product of conception to show evidence of respiration, heartbeat, or definite movement of a voluntary muscle after expulsion from the uterus, without possibility of resuscitation” should be reported to the Coordinating Center using the Vanderbilt Coordinating Center SAE form within 24 hours of the site becoming aware.

Death Neonatal. Neonatal death is defined in CTCAE as “A disorder characterized by cessation of life occurring during the first 28 days of life” that is felt by the investigator to be at least possibly due to the investigational agent or

intervention should be reported expeditiously. A neonatal death should be reported to the Coordinating Center using the Vanderbilt Coordinating Center SAE form within 24 hours of the site becoming aware

Pregnancy, Fetal Death and Death Neonatal will all be reported by the Coordinating Center to the Sponsor, Cancer Prevention Pharmaceuticals, within 24 hours of the Coordinating Center becoming aware.

CONFIDENTIAL

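### Section 15.5.1 keeps deaths from progression of disease off the SAE form, so an incident gastric cancer death could miss 24-hour reporting, contrary to the SAE definition in 15.4.2

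*Combined protocol and SAP*

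**What the plan says.** Section 15.4.2 lists fatal or life-threatening events first among the criteria for an SAE. Its exceptions concern hospitalizations only; none concerns deaths. One exception is admission for "routine treatment or monitoring of the studied indication, not associated with any deterioration in condition, or for elective procedures".

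Section 15.5.1 then gives two instructions about deaths in one paragraph. The first is general: "All deaths that occur during the protocol-specified AE reporting period, regardless of attribution, will be reported to the appropriate parties". It names neither recipient nor deadline. The second covers a subset: deaths in the reporting window "attributed by the investigator solely to progression of disease should be recorded only in the study eCRF and not reported as an SAE".

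The same section closes with a list introduced by "Hospitalizations for the following reasons do not require reporting". The last item is "Hospitalization or prolonged hospitalization for scheduled therapy of the target disease of the study".

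Neither the disease whose progression is meant nor the target disease is defined.

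The reporting route hangs on SAE status. Section 15.5.2 states: "All serious adverse events must be reported to the Coordinating Center within 24 hours of the site becoming aware of the event". Section 15.5.5 adds: "The Coordinating Center will submit all SAEs, regardless of causality, to Cancer Prevention Pharmaceuticals", again within 24 hours.

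**The concern.** In a trial treating established cancer, progression is the expected course of a disease present at entry. Here the entry condition is a premalignant lesion. Death from its progression can hardly mean anything except death from a gastric cancer that arose on study, and that is the outcome the agent is being developed to prevent (2.0 Background).

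Without an SAE form, such a death does not start the 24-hour notice to the Coordinating Center and sponsor, does not enter the DSMC's quarterly SAE review (15.2), and is not counted in the SAE rates compared between arms (12.1). Expedited FDA reporting in 15.5.4 depends on relatedness as decided by the sponsor-investigator. Under 15.5.1 the site investigator's attribution comes first and can stop the event from reaching that decision as an SAE.

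Sites that follow different sentences would also report the same event differently.

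**Working it through.** The protocol states no figure on this point, so the check sets the sections side by side.

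**Step 1. What the disease can be.** Section 5.2 requires atrophic gastritis or intestinal metaplasia and excludes every grade of dysplasia and any history of gastric cancer. The Background runs the cascade from these lesions to adenocarcinoma. An investigator could therefore class a death from incident gastric cancer as due solely to progression.

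**Step 2. Which rule governs that death.**

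| Section | Effect on an incident gastric cancer death in the window |
|---|---|
| 15.4.2 | SAE, because fatal; no exception for deaths |
| 15.5.1, general sentence | Reported whatever the attribution; route not stated |
| 15.5.1, progression sentence | eCRF only; no SAE report |
| 15.5.2 | All SAEs to the Coordinating Center within 24 hours, whatever the cause |
| 15.5.5 | All SAEs on to the sponsor within 24 hours, whatever the cause |

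A site cannot follow both 15.4.2 with 15.5.2 and the progression sentence. That is a direct conflict.

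**Step 3. Is there an efficacy reason for the exemption?** Exempting deaths can make sense when they are counted as endpoints elsewhere. Sections 1.0 and 11.0 list gamma H2AX DNA damage (primary at 6 months), the histopathology score, toxicities and candidate SNPs. No cancer-incidence or mortality endpoint appears, so the documents give no such reason.

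**Step 4. Admissions.** The closing item of 15.5.1 exempts scheduled therapy of the target disease with no condition attached. The comparable exception in 15.4.2 limits routine treatment of the studied indication to cases without deterioration. Take a planned resection of a cancer found at Month 6:

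- For reporting: 15.5.1 makes any AE leading to hospitalization an SAE, names the event behind a procedure as the SAE, and makes worsening of a pre-existing condition reportable. The 15.4.2 limit points the same way, since a cancer absent at entry is a new event or a deterioration.
- Against reporting: the exemption list follows those rules and can be read as their exception, and an undefined target disease could be taken to include gastric cancer.

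The balance favours reporting, but the text lets two sites reach different answers.

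**Step 5. Size.** Routine AE reporting ends 30 days after the last dose (15.3, Adverse Event Reporting Purpose). With 18 months of treatment the window is about 18 + 1 = 19 months. For 300 participants the most follow-up inside it is about 300 × 19/12 = 475 person-years, before dropout. The documents give neither a gastric cancer incidence nor a gastric cancer death rate, so no expected number of exempted deaths can be derived.

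**The case against.** **The two sentences on deaths in 15.5.1 can be read together.** The general one names no form or route, and the later one assigns a subset to the eCRF. This stands as far as it goes: within that paragraph there is poor fit, not flat contradiction. It does not remove the conflict with 15.4.2.

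**Nothing is lost.** Exempted deaths remain in the eCRF. Histology is recorded at every study endoscopy (4.1, 10.0), and the histopathology score, which covers dysplasia, is compared by arm. The DSMB receives reports every 6 months and may see any data it needs (15.1). Section 12.1 compares AEs as well as SAEs. This stands. A reader might infer that an excess of cancer deaths on active drug would go unseen; the documents do not support that. What is at risk is speed and inclusion in SAE review.

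**Admissions are already covered.** A reader might infer that admissions for incident cancer or dysplasia bypass SAE reporting altogether. That would require the target disease to include cancer or dysplasia and the admission to be scheduled therapy. An unscheduled or diagnostic admission does not qualify, and the other rules in 15.5.1 point to reporting. Most of this objection stands; what survives is the undefined term and the missing no-deterioration limit.

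**The wording's origin is unknown.** It may look carried over from a cancer-treatment protocol, but the documents do not say so and the point does not depend on it.

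**Conclusion.** The point holds for deaths. As written, 15.5.1 could keep an incident gastric cancer death off the SAE form, in conflict with 15.4.2 and without a listed endpoint to justify it. This assumes that an investigator reads progression along the protocol's own cascade, which is the natural reading given the entry criteria but is not a stated definition. The consequence is delay, or omission from SAE review and the SAE comparison. The record itself is kept.

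For admissions the finding is an ambiguity that could produce inconsistent site reporting; a bypass is not established.

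The number of affected deaths is expected to be very small. Multiplying person-years by an outside cancer incidence would count incident cancers, whereas the exemption covers only deaths attributed solely to progression inside a window of about 19 months. Such a figure would not measure the effect.

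A reader might also infer that every new dysplasia reading should become an SAE. That goes beyond the seriousness criteria in 15.4.2. At Month 24 it would also run into the reporting window, which after 30 days off drug takes in only events attributed to the agent.

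**What to change.** 1. In 15.5.1, delete the sentence exempting deaths attributed to progression of disease, so that every death in the reporting window follows 15.4.2 and 15.5.2.
2. In the 15.5.1 list of non-reportable hospitalizations, delete the target-disease item. Alternatively, define the term and attach the no-deterioration limit that 15.4.2 uses.
3. Read 15.4.2 and 15.5.1 together after these edits and confirm that they give one answer for a death from, and a planned admission for, a gastric cancer first found on study.

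The cost is a wording amendment and at most a few extra SAE forms. No procedure, visit or sample is added.
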